12.1 Assessments

Data will be collected by members of the research team, except for the therapists rated fidelity checklist which will be completed by therapists themselves and returned to the study team.

A schematic diagram (Figure 3) illustrates the study timelines for participants for Phase 2 only.

National

Autistic

Figure 3. Schedule of enrolment, interventions and assessments¹

Procedures	Number of Visits							
	Screening	Baseline	Treatment Phase	Follow Up				
Informed consent or advice from a Consultee	1							
Demographics	1							
Medical history	1							
Eligibility assessment	1							
Delivery of intervention			12					
Fidelity			12 (therapist completed)					
Anxiety symptoms		1		1				
Anxiety Diagnostic Checklist		1		1				
Autism Symptoms		1		1				
Emotional and Behavioural Problems		1		1				
Challenging Behaviour		1		1				
Medication		1		1				
Community Involvement		1		1				
Adverse event assessments (if required)			1	1				
Semi-structured interviews				1				

¹ Taken from the HRA CTIMP protocol template (2016).

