Setting, Context, and Study Pathway. The study will take place within NHS mental health and learning disabilities services in England (Coventry and Warwickshire Partnership NHS Trust; Worcestershire Health and Care NHS Trust, and other Trusts if necessary, to reach recruitment targets). We will nest our project within the RADiANT consortium of NHS providers working in collaboration with a number of universities. We will make use of this network to help facilitate the timely recruitment and participants into this study. For the current project, we will use a multi-point recruitment strategy incorporating specialist community teams for people with autism or intellectual disabilities, advocacy and family support groups, mental health teams, the voluntary and charitable sector, special education settings that include young adults (some schools, special education colleges), self-referral, and through our PPI partners associated networks, specifically the National Autistic Society. The steps in the pathway for the feasibility study are as follows: (a) all participants who provide consent, or participants where a Consultee, in accordance with the Mental Capacity Act, 2005, has provided advice that the participant can be included, will be screened by research staff to ensure they meet the eligibility criteria for the study, (b) following baseline assessment, participants who meet eligibility criteria will be assigned to receive the behavioural intervention plus TAU, and we aim to provide the treatment within existing services within our sites, (c) participants who receive the behavioural intervention plus TAU will have regular scheduled contact with a therapist, and we have allocated between 8 to 12 individual sessions of the intervention per participant within our current timetable, (d) participants will then be assessed using our outcome measures within 4-weeks following the completion of the intervention, (e) a subsample of participants and their carers and clinicians will be asked to take part in semi-structured interviews following the intervention process to further ascertain acceptability and the experience of the intervention the study pathway, and procedures, consent, and associated factors to create a description of factors that promote or challenge the implementation of the intervention, recognising that those with severe intellectual disabilities may not be able to take part in these interviews, meaning that we will have to rely on carers and family members, and (f) through the Study Steering Committee, make a recommendation to the funders for their consideration as to whether a future clinical trial is feasible. This decision will be made by the funder once the study results are available.

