The participant's written informed consent must be obtained using the correct Study Consent Form, which follows the Participant Information Sheet. The participant should be given up to 72 hours after the initial invitation to participate before being asked to sign the Consent Form. Informed consent must be obtained prior to the participant undergoing procedures that are specifically for the purposes of the study. Consent will taken from participants by a member of the research team.

[figure not shown]

Similarly, a consultee's advice that a participant should be included or excluded must be obtained using either the Personal or Nominated Consultee Declaration Form which follows the Information for Personal or Nominated Consultees Information Sheet. The Consultee should be given up to 72 hours, or longer, if requested, after the initial invitation to provide advice about whether the participant should be included within this research study. Signed advice to include a participant must be obtained from the Consultee prior to the participant undergoing procedures that are specifically for the purpose of the study. Advice from consultees will be taken by a member of the research team.

A copy of the consent form or Consultee Declaration form should be given to the participant or Consultee as appropriate, but the original copy should be digitised and added to the electronic investigator site file. The source data will be stored within a locked filing cabinet within a secure locked room at the University.

The right of the participant or Consultee to refuse to participate in the study without giving reasons will be respected. A participant will remain free to withdraw, and a Consultee will remain free to withdraw a participant at any time from the treatment and/or study without giving reasons and without prejudicing his/her further treatment. It is possible for a participant or their Consultee to discontinue treatment; if such occurs, data can be collected about the participant are per protocol as if they had continued to receive treatment should they wish.

Coventry and Warwickshire Partnership

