Training and Supervision. All therapists and supervisors will be required to take part in a two-day training course in the delivery of our intervention. Therapists will receive regular supervision as part of this study from qualified clinical psychologists working within services for people within intellectual disabilities who are also trained in the intervention. This will be at least two-weekly. These supervisors will receive regular supervision from members of the research team which will also be two-weekly.

Fidelity. Therapists will use a self-report fidelity checklist (a part of the manual) at the end of each session to report on, and provide data about adherence, and supervisors will be encouraged to use this checklist with their supervisees. This will be developed within Phase 1 of this study. We will look to design our fidelity checklist such that it captures both the delivery of specific components of our intervention, and which adaptations are made by therapists when tailoring the interventions to meet the individual needs of participants (e.g. using a checklist to record the adaptations made to each session from a set of pre-existing choices). Our project team has experience of developing robust fidelity ratings for psychological interventions for people with intellectual disabilities within large clinical trials (Flynn et al., 2017; Jahoda et al., 2018) and we will use this experience to help develop our checklist for this feasibility study collaboratively with our partners within Phase 1 of the research.

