13.4 Reporting procedures

13.5.1 Participating Site Responsibilities

The PI (or delegated appropriately qualified member of the study team team) should sign and date the SAE/AE Reporting Form (see Appendix) to acknowledge that they have performed the seriousness and causality assessments. Investigators should also report SAEs to their own Trust in accordance with local practice and this may involve the completion of an additional form.

A completed SAE/AE form for all events requiring immediate reporting should be submitted via email to [contact] within 24 hours of knowledge of the event. A separate form must be used to report each event, irrespective of whether the events had the same date of onset.

The participant will be identified only by participant number, partial date of birth (mm/yy) and initials. The participant's name should not be used on any correspondence.

It is also required that sites respond to and clarify any queries raised on any reported SAEs and report any additional information as and when it becomes available through to the resolution of the event. Additionally, the study team may request additional information relating to any SAEs and the site should provide as much information as is available to them in order to resolve these queries.

Serious Adverse Event (SAE) and Adverse Event (AE) email address:

[contact]

Serious adverse events and all other adverse events should be reported from time of signature of informed consent, throughout the treatment period up to, and including 40 days after the participant has stopped receiving the intervention.

An SAE/AE form is not considered as complete unless the following details are provided:

- Full participant number
- An Adverse Event
- A completed assessment of the seriousness, and causality as performed by the PI (or another appropriately medically qualified doctor registered on the delegation log).

If any of these details are missing, the site will be contacted, and the information must be provided by the site to the study team within 24 hours.

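### Figure 3's adverse event row does not match the reporting window in Section 13.5.1, and the protocol names nobody to ask about adverse events during treatment

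*Protocol*

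**What the plan says.** **Reporting window.** Section 13.5.1 states: "Serious adverse events and all other adverse events should be reported from time of signature of informed consent". The window continues through treatment and closes 40 days after the participant stops the intervention. For AEs in general the verb is *should*. Section 13 uses *must* for serious adverse events (SAEs), which the site Principal Investigator (PI) reports within 24 hours of knowing of them.

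**Schedule.** In Section 12.1, the columns of Figure 3 stand under the header "Number of Visits". The row "Adverse event assessments (if required" is blank for screening and baseline and has a 1 for the treatment phase and a 1 for follow-up. In the same treatment column, intervention delivery has 12 and fidelity has "12 (therapist completed". Section 6 says of the number of sessions: "we have allocated between 8 to 12 individual sessions of the intervention per participant". Section 12.2 provides one follow-up, within 4 weeks of completing the intervention.

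**Who collects.** Section 12.1 says: "Data will be collected by members of the research team, except for the therapists rated fidelity checklist which will be completed by therapists themselves". Section 11.2 says: "Therapists will use a self-report fidelity checklist (a part of the manual) at the end of each session". As described there, that checklist records which components were delivered and which adaptations were made. Section 13.5.1 gives the SAE/AE form to the site, signed by the PI or a delegate, and Section 16 lists that form as the source for adverse events.

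**Entry without consent.** For people who lack capacity, Section 9.4 says: "Signed advice to include a participant must be obtained from the Consultee prior to the participant undergoing procedures".

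**The concern.** A duty to report begins when somebody knows of an event. For non-serious AEs during treatment, the protocol does not say who must find out. Section 12.1 points to the research team and Section 13 points to the sites. The therapist, who is present at every session, completes a form each time that is about fidelity.

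This population makes passive reporting weak. The Synopsis wants at least one third of participants to have severe intellectual disability. Section 6 accepts that such participants may be unable to take part in interviews. Section 13.3 expects distress, possibly enough to stop a session, and a temporary rise in challenging behaviour. It expects both outside sessions as well, where a carer is the likely witness, yet nothing schedules a question to the carer during treatment.

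What is at stake is how the AE data can be read. If a form exists only when an event was volunteered, a participant who was asked and had none looks the same as one who was never asked. The count would then partly measure how forthcoming each therapist and carer was.

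**Working it through.** No power or precision figure enters this point. The check sets the schedule beside the reporting window and counts.

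**1. Entries in Figure 3 against the window in 13.5.1**

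| Interval | Reporting open under 13.5.1? | AE entries in Figure 3 |
|---|---|---|
| Screening (consent is taken here) | Yes, from signature | 0 |
| Baseline | Yes | 0 |
| Treatment phase, 8 to 12 sessions | Yes | 1, conditional |
| Follow-up, within 4 weeks | Yes | 1, conditional |
| Week 4 to day 40 | Yes | 0 |

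**2. Is the 1 shorthand for continuous collection?** The column header counts visits, and the same column gives 12 for delivery and 12 for fidelity. The authors entered per-session activity where they meant it, so the natural reading of 1 is a single occasion.

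**3. Size in the treatment phase**
- Sessions over 30 participants: 30 × 8 = 240 to 30 × 12 = 360.
- Scheduled AE enquiries: at most 30 × 1 = 30.
- If the one enquiry falls at a session, the sessions per participant without one are 8 − 1 = 7 to 12 − 1 = 11.

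**4. Recall if an early event surfaces only at follow-up.** The protocol does not state session frequency. Assuming weekly sessions, treatment takes about 8 to 12 weeks and follow-up comes 0 to 4 weeks later, which gives 8 + 0 = 8 to 12 + 4 = 16 weeks. Less frequent sessions would lengthen this. Section 12 puts total enrolment at about 6 months.

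**5. Start of the window.** Section 9.4 expects that many Phase 2 participants will lack capacity. They enter on a Consultee declaration and sign no consent form, so on a literal reading the trigger in 13.5.1 never occurs for them. The first row of Figure 3 does name both routes, which suggests an oversight in 13.5.1.

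**6. End of the window.** 4 weeks = 28 days, and 40 − 28 = 12. Reporting stays open for at least 12 days after the last possible on-schedule visit.

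**7. Who asks.** The sections read together assign the form (13.5.1), the reporting of SAEs once known (13), and general data collection (12.1). None assigns the question to the participant or carer during treatment.

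**The case against.** The strongest reply is that AE reporting here is event-driven. Section 13 makes the PI responsible for ensuring that site staff know the safety section. SAEs have a 24-hour route, and nothing limits a therapist to the fidelity checklist when an event occurs. An event-driven duty needs no visit entry, so a blank at screening or baseline does not cancel it, and the conditional label fits that design. This stands for SAEs and for any event that comes to the site's notice. It does not answer who seeks out the non-serious events.

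There are also other channels. Section 9.3 plans regular contact with participants, and Section 12 has therapists supervised at least two-weekly and their supervisors supervised two-weekly by the research team. Anxiety symptoms and challenging behaviour are measured before and after treatment, and interviews cover the experience of treatment in a subsample. These may bring events to light, but none is an AE enquiry.

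A reader might infer four stronger claims that the text does not support:
- **That treatment-phase harm has no scheduled collector.** Figure 3 has one treatment-phase entry, and 12.1 makes the research team the default collector.
- **That the research team has no contact during treatment.** Sections 9.3 and 12 say otherwise.
- **That participants mostly lack capacity.** Section 9.4 speaks of many, and of a proportion.
- **That the AE count feeds the progression decision.** The criteria in 14.7 cover recruitment, protocol adherence and outcome data, and neither they nor the outcomes in 5.2 use an AE count or threshold.

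**Conclusion.** The point holds as a mismatch inside the protocol and a gap in assignment. Figure 3 does not cover the window that 13.5.1 opens, and routine enquiry about non-serious AEs during treatment belongs to nobody in particular. On the schedule as written there are at most 30 conditional enquiries against 240 to 360 sessions, none before treatment, and at least 12 days of open reporting after the last visit. Two details are wrong as worded: the start of the window omits the Consultee route, and its end does not fit the follow-up.

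The consequence is limited to non-serious AEs and to how an AE count can be interpreted. SAEs have a working route, and no progression rule is affected. The correction should be made because it is cheap and the passive alternative is weak in this population.

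This rests on reading the 1 in Figure 3 as one occasion and on the checklist as Section 11.2 describes it. The checklist was still to be developed, and the SAE/AE form sits in an appendix that was not available. If either already contains a standard AE question at each session, the gap narrows to the wording of Figure 3, 12.1 and 13.5.1. The 8 to 16 week recall span further assumes weekly sessions.

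**What to change.** - **Figure 3:** delete the conditional label from the AE row and enter AE assessment at baseline, each treatment session and follow-up.
- **Therapist checklist:** add one standard AE enquiry, asked of the participant and the carer at each session, with its answer recorded even when it is negative. A positive answer leads to the SAE/AE form. The study team should define a positive answer against the expected events in 13.3, so that therapists apply it alike.
- **Section 12.1:** add this item to the exception for therapist-completed data, so that 12.1 and 13 agree on who collects.
- **Section 13.5.1:** start the window at informed consent or signed Consultee declaration.
- **Sections 12.2 and 13.5.1:** reconcile the 40-day window with the follow-up within 4 weeks, and state how events between the two reach the study team.

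The cost is protocol wording, one row of a figure and one item on a form already completed each session. The first four changes add no visit. The downside is more AE forms for sites and a higher reported AE count, which should be explained when results are compared with studies that relied on spontaneous reports.

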12.2 Follow-up

There is only a single follow-up period for this study which is within 4-weeks of the completion of the intervention. For participants who discontinue treatment, and wish to remain enrolled in the study, data will be captured as per protocol. This means that data will be captured within the 4-week period following when treatment would have been completed had the participant continued to take part in the intervention.

We will carry out semi-structured interviews with up to one third of patients and their carers as well as all clinicians delivering the intervention (up to n = 10) to ascertain acceptability and the experience of the treatment, the study pathway, and procedures, consent, outcome measures used, views about randomisation within a larger trial, and integrate this information to create a description of factors that promote or challenge the implementation of the intervention with reference to our logic model.

13 Safety reporting

The Principal Investigator is responsible for ensuring that all site staff involved in this study are familiar with the content of this section. This section applies only to Phase 2 of the study.

All SAEs must be reported immediately (and within 24 hours of knowledge of the event) by the PI at the participating site to Study Team unless the SAE is specified as not requiring immediate reporting (see section 13.2).

Term	Definition
Adverse Event (AE)	Any untoward medical occurrence in a participant or study participant administered an intervention which are not necessarily caused by or related to that product
Serious Adverse Event	Any adverse event that -
(SAE)	Results in deathIs life-threatening*

13.1 Definitions

Serious Adverse Reactions (SARs)	Any SAE occurring in a study participant for which there is a reasonable possibility that it is related to the intervention.								
Serious Adverse Reactions									
	 Consists of a congenital anomaly or birth defect Other medically important condition*** 								
	Results in persistent or significant disability or incapacity								
	 Required hospitalisation or prolongation of existing hospitalisation** 								

*Note: The term 'life-threatening' in the definition of serious refers to an event in which the studyl participant was at risk of death at the time of the event or it is suspected that used or continued used of the product would result in the subjects death; it does not refer to an event which hypothetically might have caused death if it were more severe.

**** Note:** Hospitalisation is defined as an inpatient admission, regardless of the length of stay, even if the hospitalisation is a precautionary measure for continued observation. Pre-planned hospitalisation e.g. for pre-existing conditions which have not worsened, or elective procedures, does not constitute an SAE.

*** Note: other events that may not result in death, are not life-threatening, or do not require hospitalisation, may be considered as an SAE when, based upon appropriate medical judgement, the event may jeopardise the participant and may require medical or surgical intervention to prevent one of the outcomes listed above.

13.2 Causality

The Principal Investigator (or another delegated qualified member of the trial team) will assess each SAE to determine the causal relationship and the Chief Investigator (or another appropriately qualified member of the Trial Management Group) can also provide this assessment where necessary:

Relationship	Description	Reasonable possibility
		that the SAE may have
		been caused by the
		intervention?

		1
Unrelated	There is no evidence of any causal relationship with the intervention	No
Unlikely	There is little evidence to suggest there is a causal relationship with the intervention (e.g. the event did not occur within a reasonable time after administration of the trial medication). There is another reasonable explanation for the event (e.g. the participant's clinical condition, other concomitant treatment).	No
Possible	There is some evidence to suggest a causal relationship with the intervention (e.g. because the event occurs within a reasonable time after administration of the trial medication). However, the influence of other factors may have contributed to the event (e.g. the participant's clinical condition, other concomitant treatments).	Yes
Probable	There is evidence to suggest a causal relationship and the influence of other factors is unlikely.	Yes
Definite	There is clear evidence to suggest a causal relationship and other possible contributing factors can be ruled out.	Yes

The causality assessment given by the Principal Investigator (or delegate) cannot be downgraded by the Chief Investigator (or delegate), and in the case of disagreement both opinions will be provided.

13.3 Expectedness

The Chief Investigator (or another delegated appropriately qualified individual) will assess each SAE to perform the assessment of expectedness.

SAEs which add significant information on specificity or severity of a known, already documented adverse event constitute unexpected events. For example, an event more specific or more severe than that described in the protocol is considered unexpected.

Expected Events				
Anxiety and/or distress	Participants are expected to experience some anxiety and/or distress associated with engagement within treatment. This could be of a nature and degree such that a treatment session must be discontinued to prevent further escalation of anxiety and/or distress. Should this happen, a graded hierarchy of fears governing exposure work would be expanded such that any associated anxiety and/or distress is lessoned. Anxiety and/or distress are expected to occur when the participant is not engaged within a treatment session with a therapist.			
Challenging behaviour	There may be a temporary increase in challenging behaviour associated with some exposure work. This should not be of a nature or degree such that others or an individual is placed at serious risk of harm. Challenging behaviours are expected to occur when the participant is not engaged within a treatment session with a therapist.			

